# 12.4. Safety Analysis

AEs will be grouped by system organ class, high level term, and preferred term according to the Medical Dictionary for Regulatory Activities (MedDRA) dictionary. Incidence by subject will be tabulated for all treatment-emergent, serious, severe, and treatment-related adverse events. Detailed listings will be provided for all serious adverse events, deaths, and withdrawals due to adverse events.

Laboratory measurements and vital signs will be summarized by treatment group at each of the protocol-specified time points.

Safety parameters will be summarized with descriptive statistics on all subjects who received at least one dose of GC4419/Placebo. Safety analyses will be conducted on the ITT population and the dosing suspension subjects separately.

Further details will be provided in the study's Statistical Analysis Plan.

# 12.5. Primary Efficacy Analysis

SOM incidence (i.e., the proportion of subjects with SOM) during the Study Treatment Period will be compared between the GC4419 and Placebo arms by the Cochran-Mantel-Haenszel (CMH) test at a 2-sided Type 1 error rate of 0.05.

Efficacy analyses will be stratified by the factors used in randomization, namely post-operative vs. definitive treatment and planned chemotherapy schedule.

Details of the primary efficacy analysis will be included in the Statistical Analysis Plan.

#### 12.5.1. Multiplicity

To control the overall Type 1 error at 0.05, the primary endpoint will first be tested at a two-sided 0.05 level. If the primary endpoint result is significant at this level, then Holm-Bonferroni multiplicity testing will be conducted on the following proposed secondary endpoints applying a familywise two-sided alpha of 0.05:

- incidence of Grade 4 OM during the Study Treatment Period:
- total number of SOM days (per subject) during the OM Observation Period for the entire study population; and

• total number of days of Grade 4 OM (per subject) during the OM Observation Period for the entire study population.

Galera Therapeutics, Inc.

Version: Amendment 4

Further details regarding multiplicity testing will be included in the Statistical Analysis Plan.

### 12.5.2. Handling of Missing Data

Subjects who withdraw consent for GC4419/Placebo administration should be encouraged to continue and complete standard IMRT/cisplatin, and protocol assessments, notably scheduled OM assessments.

Investigators should make reasonable attempts to continue to collect WHO OM scores for inclusion in the study database for subjects who discontinue from GC4419/Placebo, cisplatin, or IMRT.

The study's Statistical Analysis Plan will discuss the imputation strategy for subjects who lack WHO OM scores, who discontinue from the study without complete follow-up of WHO OM scores, and whose resolution date of severe OM is unknown.

# 12.5.3. Covariate Adjustment

Because the randomization is stratified by baseline post-operative vs definitive treatment status, and by planned cisplatin schedule, the primary analysis will be stratified by these factors. The Statistical Analysis Plan will contain guidelines for combining strata should the size of any of the four strata be unacceptably small.

# 12.6. Secondary Efficacy Analyses

## 12.6.1. Secondary Endpoints

Secondary endpoints will be analyzed as described in Section 12.5.1; testing will be stratified by the factors used in randomization.

The number of days of SOM, or of Grade 4 OM, will be determined as follows:

- Subjects who never develop SOM during the OM Observation Period will be judged to have zero days of SOM
- Subjects who never develop Grade 4 OM during the OM Observation Period will be judged to have zero days of Grade 4 OM
- For subjects who do develop SOM or Grade 4 OM, the number of days of SOM or Grade 4 OM will be taken to include all days from the first observation of SOM or Grade 4 OM to the last observation of SOM or Grade 4 OM, with no subsequent SOM or Grade 4 OM

Additional details will be described in the Statistical Analysis Plan.

## 12.7. Exploratory Efficacy Analyses

Exploratory efficacy analyses will be described in the Statistical Analysis Plan.

# 12.8. Analysis of Tumor Endpoints

# 12.8.1. Local or Regional Progression

Local (primary site) or regional (neck) progression is defined as clinical or radiographic evidence of progressive disease at the primary site or neck. The location of progressive disease should be separately distinguished (local vs. neck) if possible. Progression of local or regional disease should be confirmed by biopsy when possible but may be clinically assessed and documented in the clinical record at the judgment of the treating clinicians. Tumor reappearing with the initial and immediate adjoining anatomical region of the primary will be considered local recurrence.

Galera Therapeutics, Inc.

Version: Amendment 4

#### 12.8.2. Distant Metastasis

Clear evidence of distant metastases (lung, bone, brain, etc.): biopsy is recommended where possible. Multiple lung nodules/masses are considered distant metastases from the index cancer unless proven otherwise.

The frequencies of locoregional and distant failure will be tabulated and standard Kaplan-Meier plots of cumulative event rates will be made for time-to-event endpoints (OS, PFS, locoregional failure over time, distant metastases over time).

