## **Secondary Objectives:**

- To assess the effect of GC4419 administered intravenously (IV) on the incidence of Grade 4 OM during the Study Treatment Period in subjects receiving post-operative or definitive therapy with single-agent cisplatin plus Intensity-Modulated Radiation Therapy (IMRT) for locally advanced, non-metastatic squamous cell carcinoma (SCC) of the oral cavity or oropharynx
- To assess the effect of GC4419 administered intravenously (IV) on the total number of days of Grade 3-4 OM during the OM Observation Period in subjects receiving post-operative or definitive therapy with single-agent cisplatin plus Intensity-Modulated Radiation Therapy (IMRT) for locally advanced, non-metastatic squamous cell carcinoma (SCC) of the oral cavity or oropharynx
- To assess the effect of GC4419 administered intravenously (IV) on the total number of days of Grade 4 OM during the OM Observation Period in subjects receiving post-operative or definitive therapy with single-agent cisplatin plus Intensity-Modulated Radiation Therapy (IMRT) for locally advanced, non-metastatic squamous cell carcinoma (SCC) of the oral cavity or oropharynx
- To confirm safety and tolerability of GC4419 administered IV in subjects receiving cisplatin plus IMRT for locally advanced, non-metastatic SCC of the oral cavity or oropharynx

To evaluate potential effects of GC4419 on tumor efficacy outcomes for the study population

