#### Safety:

Safety of GC4419 as measured by:

- Frequency, duration, and severity of Adverse Events (AEs) and serious AEs
   (SAEs) during the AE Observation Period;
- Incidence and shifts of clinically significant laboratory abnormalities

Effect of treatment on tumor outcomes (locoregional failure, distant metastases, progression-free survival, overall survival) during the LTFU Observation Period

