# 6.2.3. Rationale for Tumor Follow-up and Analysis

Although the mechanism of action, existing nonclinical data (in vitro and in vivo), and existing clinical data with GC4419 uniformly indicate otherwise, there is a theoretical potential for GC4419 to protect the tumor from the therapeutic effects of concurrent chemoradiation. Patient candidates for GTI-4419-301 will be informed of this potential risk and the existing data as part of the consent process and document. GT-001 showed no evidence of tumor protection (See Investigator's Brochure). Tumor follow-up is ongoing for GT-201.

Fakhry et al. published an analysis comparing time to and patterns of progression for HPV-positive and HPV-negative patients treated in RTOG 0129 or RTOG 0522. The rate of progression was similar in the two groups. After a median follow-up of four years, the majority of progression events was found to have occurred in the first year after protocol therapy (Fakhry et al. 2014). This information suggests that tumor control data at one year after protocol treatment may provide a strong indication that results are consistent with expectations. As such, subjects in this Phase 3 trial will be followed for tumor progression for one year after completing treatment. Subjects will continue follow-up past that point for overall survival only.

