#### 10.6.3. Survival Status

Subjects will be followed for survival for two years after IMRT:

Every 3 months,  $\pm$  30 days, throughout the 1st year post-IMRT (Months 3, 6, 9, and 12)

Every 4 months,  $\pm$  30 days, throughout the 2nd year post-IMRT (Months 16, 20, and 24)

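### Section 12.8 pre-specifies no between-arm estimate or confidence interval for tumor outcomes, although the effect of GC4419 on them is a secondary objective

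*Combined protocol and SAP*

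**What the plan says.** Section 6.2.3 gives the reason for following tumor status: "there is a theoretical potential for GC4419 to protect the tumor from the therapeutic effects of concurrent chemoradiation". Section 5.1 turns this into a secondary objective: "To evaluate potential effects of GC4419 on tumor efficacy outcomes for the study population". Section 5.2 words the matching endpoint as a treatment effect: "Effect of treatment on tumor outcomes (locoregional failure, distant metastases, progression-free survival, overall survival) during the LTFU Observation Period".

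The analysis is in Section 12.8.2. For counts: "The frequencies of locoregional and distant failure will be tabulated". For OS, PFS, locoregional failure and distant metastases over time: "standard Kaplan-Meier plots of cumulative event rates will be made for time-to-event endpoints". Section 12.8.3 adds a tabulation of second primaries. The multiplicity scheme in Section 12.5.1 covers oral mucositis endpoints only. The one power statement, in Section 12.2, concerns severe oral mucositis.

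On interpretation, Section 6.2.3 says that one-year tumor control data "may provide a strong indication that results are consistent with expectations". On follow-up, the same section says that "subjects in this Phase 3 trial will be followed for tumor progression for one year after completing treatment", and Section 10.6.3 says "Subjects will be followed for survival for two years after IMRT".

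Section 12.1 leaves technical details of all analyses to a separate SAP, which prevails where the two differ. The text of that SAP is not in the supplied file.

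**The concern.** The objective and the endpoint ask how treatment changes tumor outcomes, which is a comparison between arms. The stated output is a table of frequencies and a set of curves. Nothing in the supplied text names a hazard ratio, a risk difference, a confidence interval, a margin or an expected number of tumor events. The basis for interpretation is agreement with expectations, although a randomized placebo arm is available.

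At stake is how the long-term safety result will be read. Two curves lying close together may be described as showing no tumor protection whether the data exclude a modest increase in hazard or only a near doubling. If the effect measure is chosen after the curves have been seen, that choice can be disputed.

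A smaller point concerns the type of plot. A subject who dies can no longer have a locoregional failure or a metastasis. If such deaths are treated as censored in a Kaplan-Meier analysis, one minus the estimate overstates the cumulative risk of failure.

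**Working it through.** **No plan figure to reproduce.** The documents give no event rate, power or precision for any tumor outcome.

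**Inputs.** Allocation is 3:2 (Section 12.1.1), so 0.6 of subjects are on GC4419 and 0.4 on placebo. The ITT size is 400, as 240 and 160 (Section 12.2). The total number of events D is assumed to be 10% to 30% of 400, that is 40 to 120.

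**Precision of a hazard ratio.** SE(log HR) = 1/√(D × 0.6 × 0.4). With an observed HR of 1.0, the 95% limits are exp(±1.96 × SE).

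| Events D (share of 400) | SE(log HR) | 95% CI at observed HR 1.0 |
|---|---|---|
| 40 (10%) | 1/√9.6 = 0.323 | 0.53 to 1.88 |
| 60 (15%) | 1/√14.4 = 0.264 | 0.60 to 1.68 |
| 80 (20%) | 1/√19.2 = 0.228 | 0.64 to 1.56 |
| 100 (25%) | 1/√24 = 0.204 | 0.67 to 1.49 |
| 120 (30%) | 1/√28.8 = 0.186 | 0.69 to 1.44 |

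**Events needed to exclude a given harm.** With a true HR of 1, excluding HR 1.5 with 80% probability at the two-sided 95% level needs (1.96 + 0.8416)² / (0.24 × (ln 1.5)²) = 7.849 / 0.03946, or about 199 events. That is about half of the 400 subjects.

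**Precision of a difference in proportions.** The half-width is 1.96 × √(p(1−p)(1/160 + 1/240)). At p = 0.10 it is 6.0 percentage points, and at p = 0.30 it is 9.2 points.

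**Competing risk of death.** Scheduled progression assessment ends at Month 12 (Sections 6.2.3, 10.6.1 and 10.10.2), so 12 months is the relevant horizon. Assume constant hazards of 0.20 per year for failure and 0.10 per year for death without failure. Neither value is in the documents.

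- One minus Kaplan-Meier, deaths censored: 1 − exp(−0.20) = 18.13%.
- Cumulative incidence: (0.20/0.30) × (1 − exp(−0.30)) = 17.28%.
- Difference: about 0.85 points.

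**The case against.** **The SAP may already do this.** Section 12.1 passes technical detail for every analysis to the SAP and lets it control. A reader might infer that Section 12.8 is final as written, because Sections 12.4 to 12.7 each point to the SAP and 12.8 does not. The documents do not support that inference, since the general deferral needs no local cross-reference. This objection stands as a limit: the gap is shown for the protocol text, not for the SAP.

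**The data permit the estimate.** A reader might go further and infer that the trial cannot say how much harm it excludes. That is too strong. Failure counts by arm with known denominators give a risk difference and interval directly, and the time-to-event data support a hazard ratio. What is missing is pre-specified reporting, not information.

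**The intervals measure the trial, not the omission.** This is true. Adding a Cox model leaves precision as it is, and the event counts behind the widths are assumed. The same range is also applied to OS, followed for 24 months, and to the progression endpoints, assessed for 12. The figures only show what the planned output would leave unstated.

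**No non-inferiority claim is made.** This is also true, and neither a margin nor a test is asked for here.

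**The competing-risk effect is small.** At 24 months the same assumed hazards give 1 − exp(−0.40) = 33.0% against (0.20/0.30) × (1 − exp(−0.60)) = 30.1%. A reader might infer a bias of that size, but scheduled progression assessment stops at 12 months, where the gap is under one point. The censoring of deaths is itself inferred, because Section 12.8 states no censoring rule.

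**Conclusion.** The point holds as a gap in pre-specification. The protocol sets the effect of GC4419 on four tumor outcomes as a secondary objective because of a risk that it names itself. The only analysis in the supplied text is descriptive, with no between-arm estimate or interval.

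Its size depends on event counts that the documents do not give. For 40 to 120 assumed events at 3:2 allocation, an observed hazard ratio of exactly 1.0 would still have an upper 95% limit between about 1.88 and 1.44. Curves that nearly coincide would therefore be compatible with an increase in hazard of roughly 44% to 88%, and the output as described would not show this.

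The conclusion is subject to what the separate SAP contains. The primary analysis is unaffected. The competing-risk issue is minor, about 0.85 points at 12 months under assumed hazards.

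**What to change.** In Section 12.8, and in the SAP if it is not already there:

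- For OS, PFS, locoregional failure and distant metastasis, report the hazard ratio of GC4419 to placebo from a Cox model stratified by cisplatin schedule and by post-operative versus definitive treatment, with its 95% CI.
- For the progression endpoints, a 12-month difference between arms with 95% CI is an acceptable alternative. Required imaging is sparse (Month 12 for all subjects, Month 3 for definitively treated subjects only, Section 10.6.2.2), so event times will be coarse.
- State that the result will be interpreted by the upper confidence limit and not by the similarity of the curves.
- As a minor change, plot locoregional failure and distant metastasis as cumulative incidence with death as a competing event.

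If the SAP already names such an estimate, one sentence in Section 12.8 saying so is enough. The cost is a paragraph and a table, with no new data or visits and no alpha spent. The downside is that the intervals will show limited precision.

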## 12.8.3. Second Primary Neoplasm

A solitary, speculated lung mass/nodule is considered a second primary neoplasm unless proven otherwise.

Frequency of second primary neoplasms will be tabulated.

# 12.9. Interim Analysis

No interim efficacy analysis is planned.

An independent Data Monitoring Committee (DMC) will perform periodic unblinded safety reviews while subjects in the study receive GC4419/Placebo.

## 13. ETHICS

## 13.1. Ethical Conduct of the Study

The Investigator will ensure that this study is conducted in full compliance with the principles of the "Declaration of Helsinki" (version October 2008), ICH guidelines, in particular ICH-GCP, or with the laws and regulations of the country in which the research is conducted, whichever affords the greatest protection to the study subject. The Investigator will also assure that the basic principles outlined in "ICH Guideline for Good Clinical Practice" as published in the Federal Register May 9, 1997, and all applicable Federal regulations including 21 CFR parts 50, 54, 56 and 312 are adhered to.

# 13.2. Institutional Review Board (IRB)/Independent Ethics Committee (IEC)/Research Ethics Board (REB) Approval

This protocol and any accompanying material to be provided to the subject (such as advertisements, information sheets, or descriptions of the study used to obtain informed consent)

will be submitted, by the Investigator, to an IRB/IEC/REB. Approval from the IRB/IEC/REB must be obtained, and a copy must be provided to the Sponsor or its representatives before initiating the conduct of any study procedures including screening or enrolling any patients into the study.

Galera Therapeutics, Inc.

Version: Amendment 4

No modifications or deviations from this protocol other than those that are deemed medically necessary by the Principal Investigator or designated sub-Investigator are to be made without prior, written approval by the Sponsor. Significant protocol deviations will be reported to the Sponsor and to the IRB/IEC/REB in accordance with its reporting policy.

Any modifications made to the protocol by the Sponsor after receipt of IRB/IEC/REB approval must be submitted to the committee for approval prior to implementation.

#### 13.3. Written Informed Consent

In accordance with regulatory and local IRB/IEC/REB requirements, before study procedures are performed, patients will be informed about the study and required to sign the IRB/IEC/REB approved Informed Consent Form (ICF). This form will be signed after adequate explanation of the aims, methods, objective and potential hazards of the study and prior to undertaking any study-related procedures. The Sponsor or its designee will provide an ICF template to the Investigator. The Sponsor or its designee must approve changes to the ICF template prior to submission to the IRB/IEC/REB. Informed consent will be obtained according to the applicable IRB/IEC/REB requirements. No patient is to be screened or treated until an ICF, written in a language in which the patient is fluent, has been obtained. The signed ICF will be retained with the study records. Each patient will also be given a copy of his/her signed ICF.

# **13.4.** Data Monitoring Committee (DMC)

An independent Data Monitoring Committee (DMC) will perform periodic unblinded safety reviews while subjects in the study receive GC4419/Placebo. The DMC will make recommendations regarding the conduct of the study, i.e., to continue enrollment, to hold enrollment until further review, to amend the protocol, or to stop the study early.

The details of the DMC meetings and responsibilities are outlined in a separate DMC Charter.

# 14. DIRECT ACCESS TO SOURCE DATA/DOCUMENTS

## 14.1. Study Monitoring

In accordance with ICH-GCP guidelines, the study monitor must have direct access to the Investigator's source documentation in order to verify the consistency of the data recorded in the electronic CRFs.

The monitor is responsible for routine review of the electronic CRFs at regular intervals throughout the study, to verify adherence to the protocol, and the completeness, consistency and accuracy of the data being entered on them. The monitor should have full access to any subject records needed to verify the entries on the electronic CRFs. The Investigator agrees to cooperate with the monitor to assure that any follow-up items identified in the course of these monitoring visits are resolved.

During site visits, the monitor will:

Check the progress of the study;

Review study data collected;

Conduct source document verification;

Identify any issues and address their resolution.

This will be done in order to verify that the:

Data are authentic, accurate, and complete;

Safety and rights of subjects are being protected;

Study is conducted in accordance with the currently approved protocol (and any amendments), GCP, and all applicable regulatory requirements.

The Investigator agrees to allow the monitor direct access to all relevant documents and to allocate his/her time and the time of his/her staff to the monitor to discuss findings and any relevant issues.

Galera Therapeutics, Inc.

Version: Amendment 4

# 14.2. Audits and Inspections

Authorized representatives of the Sponsor, a regulatory authority, an Independent Ethics Committee or an Institutional Review Board may visit the site to perform audits or inspections, including source data verification. The purpose of a Sponsor audit or inspection is to systematically and independently examine all study-related activities and documents to determine whether these activities were conducted, and data were recorded, analyzed, and accurately reported according to the protocol, GCP guidelines of the ICH, and any applicable regulatory requirements. The Investigator should contact the Sponsor immediately if contacted by a regulatory agency about an inspection.

## 14.3. Protocol Compliance

The Investigator is responsible for ensuring the study is conducted in accordance with the procedures and evaluations described in this protocol.

#### 14.4. Protocol Modifications

Protocol modifications, except those intended to reduce immediate risk to study subjects, may be made only by the Sponsor or its representatives. All protocol modifications must be submitted to the IRB/IEC/REB in accordance with local requirements. Approval must be obtained before changes can be implemented.

#### 14.5. Information Disclosure

# 14.5.1. Ownership

All information provided by the Sponsor or its representatives, and all data and information generated by the site as part of the study (other than a subject's medical records), are the sole property of the Sponsor.

# 14.5.2. Confidentiality

All information provided by the Sponsor or its representatives, and all data and information generated by the site as part of the study (other than a subject's medical records) will be kept confidential by the Investigator and other site staff. Information related to this study is subject to the confidentiality provisions of the Clinical Research Agreement between the investigative site and the Sponsor.

Galera Therapeutics, Inc.

Version: Amendment 4

